2.3 Benefit/Risk assessment

All study participants are expected to benefit from intensive monitoring of their blood pressure and overall health while receiving the optimal or maximally tolerated triple background antihypertensive therapy for their rHTN. Eighty percent of participants are planned to be treated with an additional antihypertensive agent (XXB750) in an effort to better control their blood pressure. The remaining participants will be treated with placebo and the duration of their treatment with placebo will be kept to a minimum, to accomplish the scientific purpose of the study. Nonetheless, the extent of this potential benefit is unknown at this time and is the primary reason for conducting this study.

As all participants are required to continue with their existing background antihypertensive medications the risk of developing severe uncontrolled hypertension during the study is expected to be minimal. Participants with a baseline office systolic blood pressure of SBP >180 mmHg are excluded from the study. Participants who develop severe uncontrolled hypertension during the study and whose SBP remains or who develop SBP >180 mmHg will be withdrawn from the study and will be managed using conventional therapies. In addition to minimize the risk due to uncontrolled hypertension participants who have experienced any significant

cardiovascular events, subjects with a history of myocardial infarction, stroke or coronary interventions, and hospitalization for hypertension crisis within the 12 months prior to study entry will be excluded from the study.

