Participants are encouraged to report any adverse events to the site between clinic visits immediately. Participants will be contacted after one week following the first dose administration and following dose escalation via a scheduled telephone call to ensure tolerability and inquire about their general wellbeing.

Should it be considered necessary, investigators may make changes to the background medications to manage symptomatic hypotension. Subjects whose symptoms and blood pressure cannot be managed by adjustments to background medications will be discontinued from the study and will be managed appropriately with open label local standard of care therapies.

XXB750 is a fully human monoclonal antibody and is not expected to elicit any significant immune response in study participants.

Participation in the study and undergoing routine study procedures may cause discomfort associated with sample collection and study drug administration. XXB750 will be administered as single 1.6 mL subcutaneous injection to the study participants. While injection site reaction is a potential local adverse event, subcutaneous injections are well tolerated in the single ascending dose study. Therefore, the risk to the participants in this study is expected to be minimal. Participants will be monitored closely for local injection site reactions and through adverse event collection. Blood samples will be taken on multiple occasions during the course of the study which may be associated with bleeding or bruising and rarely fainting and infection. However, such events are very rare and the risk to the participants in this study is expected to be minimal.

Women of child-bearing potential will be informed that taking the study treatment may involve unknown risks to the fetus if pregnancy were to occur during the study and agree that in order to participate in the study they must adhere to the contraception requirements outlined in the exclusion criteria. If there is any question that the participant will not reliably comply, they should not be entered or continue in the study. In general, the levels of a mAb in semen are expected to be low, and therefore the subsequent levels in female partner would be negligible. Based on this principle, the probability that XXB750 would cause teratogenicity is very low. Therefore, no restrictions will be placed on male participants with regard to sexual activity or condom use.

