6.4.1 Recommended treatment of potential anticipated adverse events

described Recommendations for handling hypertension and hypotension are in Section 6.5.3 and Section 10.7, respectively.

Recommendations for handling Liver events are described in Section 10.5.1

Recommendations for handling potential drug induced liver injury (DILI) cases are described in Section 6.5.4.1

Recommendations for handling Renal events are described in Section 10.6.1

Medication used to treat adverse events (AEs) must be recorded on the appropriate CRF.

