6.5.3 Dose modifications

Except for force up-titration of study medications outlined in Section 6.5.1.1, Investigational study treatment dose adjustments and/or interruptions are not permitted. Participants who are considered to be intolerant to study medications should discontinue study treatment.

Safety criteria determining dose interruption or discontinuation based on liver or renal events are listed in Appendix 5 (Section 10.5) and Appendix 6 (Section 10.6), respectively. Deviations from mandatory dose interruptions and/or reductions are not allowed.

If the participant experiences severe hypertension (defined as SBP > 180 mmHg confirmed by 3 readings 5 minutes apart), consider discontinuing all study medication and starting the subject on open label treatment accompanied by monitoring of BP as per local standard of care until the doses of the new medications are stable and BP is under control.

Dose modifications of background therapy

Dose adjustments of any component(s) of the background antihypertensive therapy medications and study medication due to hypotension are listed in Section 10.7.

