7.1 Discontinuation of study treatment

Discontinuation of study treatment for a participant occurs when study treatment is permanently stopped for any reason (prior to the planned completion of study treatment administration) and can be initiated by either the participant or the Investigator.

The Investigator must discontinue study treatment for a given participant if he/she believes that continuation would negatively impact the participant's well-being.

Discontinuation from study treatment is required under the following circumstances:

- Participant/guardian decision
- Pregnancy
- Use of prohibited treatment as per recommendations in the prohibited treatment section
- Participants who develop severe uncontrolled hypertension during the study and whose SBP remains >180 mmHg.
- Any situation in which continued study participation might result in an unacceptable safety risk to the participant. This includes adverse events, liver (Section 10.5) and renal (Section 10.6) events as described in the corresponding sections, as well as intolerance to investigational study drugs.
- Following emergency unblinding

The reasons for discontinuation from study treatment must be collected.

^{**}Regular use of bronchodilators for asthma/COPD is acceptable but must be documented.

If discontinuation from study treatment occurs, the Investigator should make a reasonable effort to understand the primary reason for the participant's discontinuation from study treatment and record this information.

Participants who discontinue from study treatment agree to return for the end of treatment and follow-up visits indicated in Section 1.3 Schedule of Assessment.

If the participant cannot or is unwilling to attend any visit(s), the site staff should maintain regular telephone contact with the participant, or with a person pre-designated by the participant. This telephone contact should preferably be done according to the study visit schedule.

After discontinuation from study treatment all efforts should be made to continue follow-up as per study design; at a minimum, in abbreviated visits, the following data should be collected at clinic visits or via telephone/email contact:

- New / concomitant treatments
- Adverse Events / Serious Adverse Events

The Investigator must also contact the IRT to register the participant's discontinuation from study treatment.

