7.2 Participant discontinuation from the study

Discontinuation from study is when the participant permanently stops receiving the study treatment, and further protocol-required assessments or follow-up, for any reason.

If the participant agrees, a final evaluation at the time of the participant's study discontinuation should be made as detailed in Section 1.3 Schedule of Activities.

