10.2.2 Definitions

Assessment	A procedure used to generate data required by the study	
Biologic Samples	A biological specimen including, for example, blood (plasma, serum), saliva, tissue, urine, stool, etc. taken from a study participant	
Clinical Trial Team	A group of people responsible for the planning, execution and reporting of all clinical trial activities. Examples of team members include the Study Lead, Medical Monitor, Trial Statistician etc.	
Coded Data	Personal Data which has been de-identified by the investigative center team by replacing personal identifiers with a code.	

Discontinuation from study	Point/time when the participant permanently stops receiving the study treatment and further protocol required assessments or follow-up, for any reason. No specific request is made to stop the use of their samples or data.	
Discontinuation from study treatment	Point/time when the participant permanently stops receiving the study treatment for any reason (prior to the planned completion of study intervention administration, if any). Participant agrees to the other protocol required assessments including follow-up. No specific request is made to stop the use of their samples or data.	
Electronic Data Capture (EDC)	Electronic data capture (EDC) is the electronic acquisition of clinical study data using data collection systems, such as Web-based applications, interactive voice response systems and clinical laboratory interfaces. EDC includes the use of Electronic Case Report Forms (eCRFs) which are used to capture data transcribed from source data/documents used at the point of care	
Estimand	As defined in the ICH E9(R1) addendum, estimand is a precise description of the treatment effect reflecting the clinical question posed by the trial objective. It summarizes at a population-level what the outcomes would be in the same participants under different treatment conditions being compared. Attributes of an estimand include the population, variable (or endpoint) and treatment of interest, as well as the specification of how the remaining intercurrent events are addressed and a population-level summary for the variable.	
Intercurrent events	Events occurring after treatment initiation that affect either the interpretation or the existence of the measurements associated with the clinical question of interest.	
Investigational drug/ treatment	The drug whose properties are being tested in the study	

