10.7 Appendix 7: Managing hypotension

As a general guidance the following events require action:

Persistent symptomatic hypotension regardless of blood pressure readings

Ensure the participant's hydration status is adequate and that there is no other clinical reason for hypotension that may need attention.

If appropriate, adjust any non background antihypertensive concomitant medications potentially contributing to hypotension (e.g., tricyclics, hypnotic sedatives, beta blockers for non-CV disorders, etc.) and increase sodium intake by favoring salty foods.

If the above interventions do not resolve the hypotension AE, adjust the doses of one or more background medicines as necessary depending on participant's tolerability profile and laboratory assessments. Investigator should exercise best clinical judgement based on laboratory assessments, volume status and any other clinical considerations in individual subjects.

If hypotension persists and no further action can be taken with background therapy, the study

drug should be withdrawn. No down titration of study drug dose is allowed.

XXB may increase the risk of prolonged hypotension in case of acute hemorrhage or hypovolemia. Subjects should be managed with appropriate fluid replacement and should be carefully monitored for hemodynamic stability. There is no antidote to XXB available at this time. Diuretics, RAS blockers, and CCBs may be stopped and resumed when hypotension is resolved.

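### Protocol Section 2.3 takes participants out of the study for SBP above 180 mmHg or for hypotension that background changes cannot control, where the operative sections act on study drug only

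*Protocol*

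**What the plan says.** **Severe hypertension.** Section 2.3 (Benefit/Risk assessment) says of participants with severe uncontrolled hypertension that those "whose SBP remains or who develop SBP >180 mmHg will be withdrawn from the study and will be managed using conventional therapies". Section 6.5.3 covers severe hypertension, "defined as SBP > 180 mmHg confirmed by 3 readings 5 minutes apart), consider discontinuing all study medication". Section 7.1 lists, among the circumstances in which study treatment must be stopped: "Participants who develop severe uncontrolled hypertension during the study and whose SBP remains >180 mmHg".

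**Hypotension.** Section 2.3 says that those whose symptoms and blood pressure "cannot be managed by adjustments to background medications will be discontinued from the study". Section 10.7 says that, if hypotension persists and background options are used up, the study "drug should be withdrawn. No down titration of study drug dose is allowed".

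**Which text sites are sent to.** Section 6.4.1 says: "Recommendations for handling hypertension and hypotension are in Section 6.5.3 and Section 10.7, respectively".

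**Definitions.** Section 7.2: "Discontinuation from study is when the participant permanently stops receiving the study treatment, and further protocol-required assessments or follow-up, for any reason". For stopping study treatment alone, Section 10.2.2 says the opposite about follow-up: "Participant agrees to the other protocol required assessments including follow-up". Section 4.1 adds that coming off study medication does not mean leaving the study unless consent is withdrawn.

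**The concern.** Study exit and drug discontinuation are separate outcomes in this protocol, and the analysis depends on the difference. The primary estimand (Protocol Section 3.1) applies a treatment-policy strategy to treatment discontinuation, so blood pressure measured after drug is stopped belongs in the analysis. Missing Week 12 values after an intercurrent event are imputed from participants in the same arm who had the same type of event and were still measured (Protocol Section 9.3.3, SAP Section 2.5.3). Both events in Section 2.3 are themselves blood-pressure outcomes. If a site ends participation at that point, the participants lost are among those whose later readings the method is meant to use, and the donor pool for the imputation shrinks as well.

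**Working it through.** The plan gives no figure to reproduce. The check is a comparison of texts, followed by day arithmetic on the visit schedule.

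**Step 1: the instructions side by side**

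| Event | Section 2.3 | Operative sections |
|---|---|---|
| Severe hypertension, SBP >180 mmHg | Leaves the study (mandatory) | 6.5.3: consider stopping study medication; 7.1: stop study treatment (mandatory) if SBP stays high |
| Hypotension not controlled through background therapy | Leaves the study (mandatory) | 10.7: study drug withdrawn |

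Sections 6.5.3 and 7.1 can be read as graduated steps. Neither says the participant leaves the study, and neither does Section 10.7.

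**Step 2: what each outcome leaves in the data.** A participant who leaves the study is offered a final evaluation, if he or she agrees, with the assessments of Visit 1999 (Sections 1.3 and 8). In Table 1-2 the ABPM row is marked at Visits 30, 160 and 170 only, so that final visit has no ABPM. Section 8.3.1 could still yield one early recording when drug is stopped. A participant who stops drug only continues all visits and procedures under Sections 4.1 and 6.8.1.

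**Step 3: effect on the imputation.** With few or no observed donors after the same event in an arm, the plan pools that arm with lower dose groups. If donors are still too few, it uses placebo (Protocol Section 9.3.3, SAP Section 2.5.3). Study exits move the analysis towards these fallbacks.

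**Step 4: is Day 84 covered after drug-only discontinuation?** Table 1-2 has doses on Days 0, 28 and 56, and Week 12 on Day 84. Sections 1.3 and 8 bring the end-of-treatment visit (Visit 170) forward once drug is stopped. The safety follow-up text of Section 4.1 places Visits 180 and 1999 at 8 and 12 weeks, that is 56 and 84 days, after the last dose:

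- Last dose Day 0: Visit 180 on 0 + 56 = Day 56; Visit 1999 on 0 + 84 = Day 84.
- Last dose Day 28: Visit 180 on 28 + 56 = Day 84; Visit 1999 on 28 + 84 = Day 112.
- Last dose Day 56: Visit 180 on 56 + 56 = Day 112; Visit 1999 on 56 + 84 = Day 140, as in Table 1-2.

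On this timing, a participant who stops after one or two doses attends on Day 84 a visit for which Table 1-2 lists no ABPM. Section 8 instead times every visit from Visit 100, and Sections 4.1 and 6.8.1 keep visits as planned. Whether a second ABPM is recorded on Day 84, after the early one, depends on which passage the site follows.

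**The case against.** The best defence is that Section 2.3 is narrative. Section 6.4.1 names the handling text, Section 4.1 says that stopping medication is not leaving the study, and Sections 6.8.1 and 7.1 agree. This stands in part: most sites would probably follow the operative sections. It does not cancel the conflict. Section 2.3 is worded as mandatory, nothing in the available text says which section prevails, and the pointer in Section 6.4.1 omits Section 7.1.

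Several stronger readings are tempting, and the documents do not support them:

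- A reader might infer three competing hypertension triggers. The Section 2.3 sentence is garbled and shares with Section 7.1 the qualifier of severe uncontrolled hypertension. It may be a slip of the same sentence, so the firm difference is in the consequence. What counts as SBP remaining high is, however, not defined.
- A reader might infer that follow-up after drug discontinuation shrinks to telephone contacts. Section 7.1 asks for every effort to follow up per design and sets abbreviated contacts only as a minimum.
- A reader might infer a shortfall in safety data. Sections 8.6.1 and 8.6.3 run adverse event and SAE collection to the end-of-study visit or 3 months after the last dose, whichever is longer, and a final evaluation is offered to those who leave.
- A reader might infer that an early end-of-treatment ABPM can never count as Week 12. Protocol Section 9.3.7 names that reading as the Week 12 assessment only in a supplementary analysis. SAP Section 2.5 covers the choice among several valid readings at a visit. Neither says how a single early reading is classified in the primary analysis.

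The events may also be few. Section 2.3 expects the risk of severe uncontrolled hypertension to be minimal, and Section 5.2 excludes office msSBP of 180 mmHg or more and 24-hour SBP above 170 mmHg at Visit 30.

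**Conclusion.** The inconsistency is real and should be corrected. For two blood-pressure events, Section 2.3 ends study participation where the operative sections end, or consider ending, study drug only. By the protocol's own definitions these outcomes leave different data behind.

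Its effect cannot be sized. The documents give no rate for either event, missing values are imputed, and nothing shows how many sites would follow Section 2.3. A reader might infer a bias that differs by arm, with high pressure on placebo and hypotension on the top dose. That is plausible but cannot be derived from the plan. Nor can missing Week 12 data be attributed to Section 2.3 alone, because the Day 84 ABPM is also unclear after drug-only discontinuation.

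A separate, minor inconsistency should not be counted here. Table 6-6 interrupts and resumes study drug for sacubitril/valsartan, while Section 6.5.3 does not permit interruptions and Section 4.1 forbids changes to the regimen. It has no study-exit consequence and needs its own reconciliation.

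**What to change.** The sponsor must reconcile Section 2.3 with Sections 6.5.3 and 7.1 for SBP above 180 mmHg, and Section 2.3 with Section 10.7 for hypotension. Each event should end with one trigger and one stated consequence, naming study drug or study. Which clinical rule applies is the sponsor's choice.

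The sponsor should also bring Sections 1.3, 7.1, 8 and the safety follow-up text of Section 4.1 into line with the continued-visit statements in Sections 4.1 and 6.8.1 and with the Visit 100 anchor in Section 8. The aligned text should state whether participants who stop drug without withdrawing consent have an ABPM on the scheduled Week 12 date, in addition to the early end-of-treatment recording.

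The cost is a written amendment with the approvals in Section 10.1.8.1. If the sponsor reads the present text as not requiring the Day 84 recording and decides to require it, early discontinuers would have one further ABPM.

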3.1 Primary estimands

The primary clinical question of interest is: Is there a dose-response signal with respect to the dose-response relationship of XXB750 30 mg SC q4w, 60 mg SC q4w, 120 mg SC q4w, and 240 mg SC q4w versus placebo in reducing the mean 24hr SBP at Week 12 from randomization in participants with rHTN, regardless of discontinuation from study treatment, regardless of change in the dose of allowed background antihypertensive medications and regardless of receiving prohibited concomitant medication?

The justification for the primary estimand is that it will capture both the effect of the tested treatments and the effect of additional standard concomitant medications, mirroring the conditions in clinical practice.

The primary estimand is described by the following attributes:

- 1. Population: participants with rHTN receiving allowed concomitant medications defined in study population (Section 5).
- 2. Variable: change from baseline in mean 24hr SBP at Week 12.
- 3. Treatment of interest: the randomized treatments (XXB750 30 mg SC q4w, 60 mg SC q4w, 120 mg SC q4w, 240 mg SC q4w or placebo) with allowed antihypertensive concomitant medications.

Handling of remaining intercurrent events:

- 1. Discontinuation of study treatment: ignore (treatment policy strategy).
- 2. Unforeseen change in the dose of allowed concomitant medications: ignore (treatment policy strategy).
- 3. Receiving prohibited concomitant medication: ignore (treatment policy strategy).

The summary measure is the difference in variable means between treatments.

3.2 Secondary estimands

Difference between highest XXB750 dose group versus placebo in change from baseline in mean 24-hour SBP at Week 12

The estimand of the first secondary objective in terms of attributes will be the same as described for the primary estimand (Section 3.1) except for the treatment of interest, which is restricted to the highest XXB750 dose group and placebo only.

This estimand will further demonstrate the efficacy of XXB750 highest dose group compared with placebo and provide an estimate with a p-value in a hierarchical hypothesis testing procedure with overall type I error control after a dose-response signal is established in the primary objective.

Difference between highest XXB750 dose group versus placebo in average of changes from baseline in mean 24-hour SBP at Week 9 and at Week 12

The estimand of the second secondary objective in terms of attributes are the same as described for the primary estimand (Section 3.1) except for (1) the treatment of interest which is restricted to the highest XXB750 dose group and placebo only; and (2) for variable which is average change from baseline in mean 24hr SBP at Week 9 and at Week 12.

This estimand will demonstrate the overall efficacy of XXB750 highest dose group compared with placebo in terms of average change from baseline at Week 9 (approximate peak state) and at Week 12 (approximate trough state) and provide an estimate with a p-value in a hierarchical hypothesis testing procedure with overall type I error control after efficacy in primary and first secondary objectives are established.

Dose-response signal and dose-response relationship of XXB750 dose groups versus placebo with respect to the proportion of participants achieving blood pressure (BP) control at Week 12

The third secondary question of interest is: What is dose-response signal and assess the dose-response relationship of XXB750 30 mg SC q4w, 60 mg SC q4w, 120 mg SC q4w, and 240 mg SC q4w versus placebo with respect to the proportion of participants achieving BP control at Week 12 in patients with rHTN without any premature discontinuation from study treatment and without any increase in the dose of allowed background antihypertensive medications nor receiving any prohibited medications.

The key secondary estimand is described by the following attributes:

- 1. Population: participants with rHTN receiving allowed concomitant medications defined in study population (Section 5).
- 2. Variable: participant's achievement of blood pressure control defined as mean 24hr SBP <130 mmHg and mean 24hr DBP <80 mmHg at Week 12.
- 3. Treatment of interest: the randomized treatment XXB750 30 mg SC q4w, 60 mg SC q4w, 120 mg SC q4w, 240 mg SC q4w or placebo.

Handling of remaining intercurrent events:

- 1. Discontinuation of study treatment: imputed as not achieving BP control (composite strategy).
- 2. Unforeseen increase in the dose of allowed concomitant medications: imputed as not achieving BP control (composite strategy).
- 3. Receiving prohibited concomitant medication: imputed as not achieving BP control (composite strategy).

The summary measure is the difference in proportions between treatments.

Evaluating the safety and tolerability of XXB750 regimens over 12 weeks of treatment and up to 20 weeks of follow-up

Adverse events (AEs) and serious AEs, laboratory parameters and vital signs will be evaluated and summarized in each treatment group for different treatment periods (run-in, randomized treatment period and post-treatment safety follow-up). Please refer to Section 9.4.2 for analysis details.

4 Study design

